**Table 21: ECG Collection During Phase 2 Dose Expansion**

Cycle	Day	Time	Comment
Screening	-28 to -1	Anytime	
1	1	Pre-dose/0h a	
1	1	Post-dose 2h	
1	1	Post-dose 4h	
1	8	Pre-dose/0h a	
1	8	Post-dose 2h	
1	8	Post-dose 4h	
1	15	Pre-dose/0h a	
1	15	Between 2-4 hours post-dose	
2-6	1	Pre-dose/0h a	
During treatment after Cycle 6	Any day b	Anytime	
End of Treatment	--	--	

All measurement times are relative to dose of DS-1594b unless otherwise specified.

a Pre-dose assessment should be taken prior to the next administration of DS-1594b and within 15 minutes prior to PK collection.

b ECG should be performed only if clinically indicated.

## 8.6. Correlative Studies (Mandatory for Phase 1)

Tumor tissue, blood samples and bone marrow aspirate/biopsy for correlative research will be collected. Correlative laboratory studies will be conducted under this clinical trial as described:

- **Peripheral blood** up to 40 mL (within 24 hours) will be collected for testing of biomarkers at Baseline (prior to day 1 dose of drug), and on Cycle 1 Days 8 ( $\pm 2$ ), 15( $\pm 2$ ), 21( $\pm 2$ ), 28( $\pm 2$ ), and on Cycle 2, Day 15( $\pm 2$ ), and Cycles 3 and 4, Day 1( $\pm 2$ ) and at end of treatment / progression (if possible). Additional timepoints may be collected as needed.
- **Bone marrow** samples will be collected for testing of biomarkers at baseline, on Day 28 (+/- 4 days), at Day 28 (+/- 4 days) of Cycles 2, 3, 6, 9, and at end of treatment or progression (if possible). Additional timepoints may be collected as needed.

- All subjects are also routinely monitored for MRD by multiparametric flow cytometry and RT-PCR or NGS (in some cases, when applicable) at the time of bone marrow assessments. This will allow an analysis of response beyond hematologic criteria and correlation with long-term outcome.
- All subjects will be evaluated by a pre-therapy and on-treatment NGS molecular panels, FISH, routine karyotyping, immunophenotyping and by a leukemia fusion panel (as applicable), to investigate correlations of gene alterations with long-term outcome, and to identify molecular characteristics of residual or recurrent clones.
- Identification of clonal subsets in AML almost entirely been done using genomics, in which cellular populations are inferred. In order to effectively characterize and ultimately treat these cells, we need tools to identify therapy resistant cell populations as they arise in subjects. Flow cytometry is a useful tool for tracking cells in subjects but traditional fluorescent cytometry is limited by panel size and scope. CyTOF (Cytometry by Time of Flight), is a variation of flow cytometry in which antibodies are labeled with heavy metal ion tags rather than fluorochromes. This allows for the combination of many more antibody specificities in a single cell with greater depth and breadth of phenotypic and functional cytometric profiling. CyTOF will enable us to identify individual treatment-resistant cell populations and their signaling state in disease relate to clinical outcomes. CyTOF will be performed on bone marrow samples and peripheral blood at screening, remission, longitudinal samples on study, and relapse (where possible).
- To enable the characterization of genetic heterogeneity in tumor cell populations, we will use novel microfluidic approach that barcodes amplified genomic DNA from thousands of individual leukemia cells confined to droplets. The barcodes are then used to reassemble the genetic profiles of cells from next-generation sequencing data. By using this approach, we will sequence longitudinally collected AML tumor populations from subjects and genotype disease relevant loci across thousands of individual cells. Targeted single-cell sequencing is able to sensitively identify cells harboring pathogenic mutations during complete remission and uncovered complex clonal evolution within AML tumors that are not observable with bulk sequencing. We anticipate that this approach will make feasible the routine analysis of AML heterogeneity, leading to improved stratification and therapy selection for the subjects. Single cell sequencing will be performed on bone marrow samples at screening, remission, longitudinal samples on study, and relapse (where possible).
- Additional analysis including but not limited to bulk RNA sequencing to include Menin dependent genes (MEIS1, PBX3, MEF2C, and others), single cell RNA sequencing, IHC for differentiation markers on bone marrow slides/blocks, plasma inhibitory activity (PIA), RT-MLP, genomic break point sequencing may be performed on the subjects' bone marrow samples and peripheral blood at screening, remission, longitudinal samples on study, and relapse (where possible).

## **8.7. Outside Physician Participation During Treatment**

- The first cycle (28 days) of DS-1594b must be administered at the site, either in-patient or out-patient. The first 7 days of azacitidine and first cycle of mini-HCVD infusions must be administered at the site. Subsequently, subjects will have the option of receiving azacitidine injections or mini-HCVD infusions at the site out-patient clinic or the local ambulatory treatment center/outside physician's office. We do not intend for the subjects to receive DS-1594b at any time at an outside physician's office. During the first cycle in both Dose Escalation and Dose Expansion of Phase 1 all the laboratory evaluations will be done at the site and the subjects must stay locally within easy access of the site. Subsequently, the subject may have the laboratory work done at a local clinic and the results reported and filed by the site research nurse for the study. The laboratory work done at the local clinic will be forwarded to the investigator or PI of the study, who will sign off on the labs to verify that the results have been reviewed.
- Investigator communication with the outside physician is required prior to the subject returning to the local physician.
- This will be documented in the subject record.
- A letter to the local physician outlining the subject's participation in a clinical trial will request local physician agreement to supervise the subject's care.
- Protocol required evaluations outside of the site will be documented by telephone, fax or e-mail. Fax and/or e-mail will be dated and signed by the Investigator, indicating that they have reviewed it. Changes in drug dose and/or schedule must be discussed with and approved by the Investigator, or they're representative prior to initiation, and will be documented in the subject record.
- A copy of the informed consent, and treatment schema and evaluation during treatment will be provided to the local physician.
- Documentation to be provided by the local physician will include progress notes, reports of protocol required laboratory and diagnostic studies and documentation of any hospitalizations.
- The home physician will be requested to report to the Investigator all life-threatening events within 24 hours of documented occurrence.
- All protocol required follow-up visits will be performed at the site.
- Changes in drug dose and/or schedule must be discussed with and approved by the investigator, or they're representative prior to initiation, and will be documented in the subject record.
- Subjects with an objective response at completion of active study treatment will be followed for survival at the site every 3 to 6 months for up to 5 years after completion of active treatment and while still on study. If the subject is unable to return to the site, the duration visits may be conducted via telephone.

- Data regarding adverse events will be collected during the study. Protocol specific data will be entered into the electronic case report form (eCRF). The eCRF used for this protocol will be Prometheus. AEs will be recorded in the Case Report Form.
- Treatment may be discontinued for a variety of reasons, including subject withdrawal, investigator decision, and reasons specified by the protocol. Reasons for discontinuation of treatments are described in section 10.0.

## **8.8. CRITERIA FOR RESPONSE:**

### **8.8.1. Response Criteria for AML**

Responses will be assessed by the criteria below, adapted from the International Working Group for AML and the European Leukemia Net Guidelines. Responders are subjects who obtain a CR, CRh, CRi, or PR, with or without cytogenetic response, or a morphologic leukemia-free state.

#### **Complete remission (CR)**

- Peripheral blood counts: No circulating blasts.
- Neutrophil count:  $>1.0 \times 10^9/L$
- Platelet count  $>100 \times 10^9/L$ .
- Bone marrow aspirate and biopsy:  $< 5\%$  blasts.
- No Auer rods.
- No extramedullary leukemia

#### **Complete remission with incomplete blood count recovery (CRi)**

- Peripheral blood counts: No circulating blasts
- Neutrophil count:  $<1.0 \times 10^9/L$ , OR
- Platelet count:  $<100 \times 10^9/L$
- Bone marrow aspirate and biopsy:  $<5\%$  blasts
- No Auer rods
- No extramedullary leukemia

#### **Complete Remission with Partial Hematological Recovery (CRh)**

- Peripheral blood counts: No circulating blasts
- Neutrophil count:  $\geq 0.5 \times 10^9/L$
- Platelet count:  $\geq 50 \times 10^9/L$
- Bone marrow aspirate and biopsy:  $< 5\%$  blasts
- No Auer rods

- No extramedullary leukemia

**Partial remission (PR)**

- Neutrophil count:  $>1.0 \times 10^9/L$
- Platelet count  $>100 \times 10^9/L$
- $\geq 50\%$  reduction in bone marrow blast from pretreatment baseline, but still  $\geq 5\%$

**Morphologic leukemia-free state (MLFS):**

- Bone marrow  $< 5\%$  myeloblasts,
- No Auer rods,
- No extramedullary leukemia,
- Neutrophil or platelet recovery is not required

**8.8.2. Response Criteria for ALL**

**Complete Remission (CR)**

- No circulating lymphoblasts or extramedullary disease
  - No lymphadenopathy, splenomegaly, skin/gum infiltration/testicular mass/CNS involvement
- Trilineage hematopoiesis (TLH) and  $<5\%$  blasts
- Neutrophil count:  $>1.0 \times 10^9/L$
- Platelet count  $>100 \times 10^9/L$
- No recurrence for 4 weeks

**Complete Remission with Partial Hematological Recovery (CRh)**

- No circulating lymphoblasts or extramedullary disease
  - No lymphadenopathy, splenomegaly, skin/gum infiltration/testicular mass/CNS involvement
- Neutrophil count:  $\geq 0.5 \times 10^9/L$
- Platelet count:  $\geq 50 \times 10^9/L$
- Trilineage hematopoiesis (TLH) and  $<5\%$  blasts
- No recurrence for 4 weeks

**Complete Remission with Incomplete Hematologic Recovery (CRi)**

- Meets all criteria for CR except platelet count or ANC

#### **8.8.3. Transfusion Independence (TI)**

TI is defined as the absence of red blood cell and platelet transfusions for a consecutive 56-day period during continued treatment.

TI will be assessed as a response achieved in the subgroup of subjects who were transfusion dependent (TD) at baseline (conversion from TD to TI with treatment) separately from the subgroup of subjects who were TI at baseline (maintenance of TI with treatment). Transfusion dependence at baseline is based on the receipt of any red blood cell or platelet transfusions within at least 28 days prior to the start of study treatment. Analyses of red blood cell TI and platelet TI will also be assessed separately.

#### **8.8.4. Relapse Definition (AML and ALL)**

Hematological relapse is defined as marrow blasts  $\geq 5\%$  by morphology, persistent reappearance of blasts in the peripheral blood by morphology, or the occurrence of extramedullary disease after achieving remission (CR, CRh, CRI, or MLFS).

When relapse is suspected on the basis of the follow-up physical examination or peripheral blood counts, additional testing may be performed to confirm the finding, but the date of relapse is set to the date of the first test that suggests relapse.

### **8.9. DISCONTINUATION OF TREATMENT**

#### **8.9.1. Discontinuation Criteria for Individual Subjects**

##### **Subject Withdrawal**

Subjects may voluntarily withdraw consent to participate in the clinical study at any time and without giving any reason. For subjects who withdraw consent, the Investigator may search publicly available records (where permitted) to ascertain survival status. Their withdrawal will not jeopardize their relationship with their healthcare providers or affect their future care.

Subjects may also choose to withdraw from study treatment but agree to remain in the study for follow-up procedures.

##### **Investigator Discontinuation of Subject**

The Investigator may exercise medical judgment to discontinue study treatment if clinically significant changes in clinical status or laboratory values are noted.

##### **Criteria for Protocol-Defined Required Discontinuation of Treatment**

The protocol requires discontinuation of study treatment for the following reasons:

- Lack of clinical benefit (defined as failure to achieve a PR or  $\geq 50\%$  reduction in bone marrow blast from pretreatment baseline within 6 cycles of treatment)
- Subject requests discontinuation.
- Unacceptable toxicity that in the opinion of the investigator makes it unsafe to continue therapy.
- Clinically significant progressive disease.

- Investigator discretion.

#### **Follow-Up at Treatment Discontinuation or Early Withdrawal**

Subjects who discontinue treatment for any reason should complete end-of-treatment procedures when possible. End of treatment procedures will include a physical examination, CBC with differential and platelets, triplicate ECG, and full chemistry panel with ALT, AST, bilirubin (fractionated), alkaline phosphatase, potassium, magnesium, creatinine kinase (fractionated if >ULN), blood urea nitrogen (BUN), serum creatinine, troponin. A bone marrow aspiration and biopsy may be recommended only if non-response or progressive disease cannot be unequivocally diagnosed from peripheral blood. Although treatment will be discontinued at that time, all subjects who do not withdraw consent for follow-up, die, or become lost to follow-up, will remain on study for follow-up evaluations. Subject will be followed for toxicity for at least 30 days after the last protocol treatment. The 100-day follow-up visit (+ or - 5 days) will be scheduled as a clinic visits for clinical evaluation and physical examinations. If the subject cannot make it to the site for this visit, the required follow up treatment procedures may be done with a local physician and the records forwarded to Investigator. The Investigator or delegate will contact the subject by telephone and get a verbal assessment of the subject's condition. The phone conversation will then be documented in the subject's charts.

#### **8.9.2. Study Stopping Rules**

The Principal Investigator and the Sponsor have the right to terminate this clinical study at any time. The principal investigator will be involved in any decisions regarding terminating the study, temporarily suspending enrollment, or stopping ongoing treatment with study treatment.

Reasons for terminating the clinical study or a study site's participation include, but are not limited to, the following:

- The incidence or severity of an adverse reaction related to treatment in this study or other studies indicates a potential health hazard to subjects
- Data recording is significantly inaccurate or incomplete
- Study site personnel are noncompliant with study procedures
- Pattern of noncompliance is observed

#### **8.9.3. Protocol Violations and Deviations**

Protocol violations are defined as significant departures from protocol-required processes or procedures that affect subject safety and benefit potential or confound assessments of safety or clinical activity. A protocol deviation is a departure from the protocol that does not meet the above criteria. Protocol violations or deviations may be grouped into the following classes:

- Enrollment criteria
- Study activities (missed evaluations or visits)
- Noncompliance with dose or schedule, including dose calculation, administration, interruption, reduction, or delay; or discontinuation criteria

- Investigational product handling, including storage and accountability
- Informed consent and ethical issues

## **8.10. ADVERSE EVENT MONITORING, RECORDING, AND REPORTING**

### **8.10.1. Definitions and Procedures**

**Adverse Event** (AE) is any untoward medical occurrence that may present during treatment with a pharmaceutical product, but which does not necessarily have a causal relationship with this treatment. **Adverse drug reaction** (ADR) is a response to a drug which is noxious and unintended, and which occurs at doses normally used in man for prophylaxis, diagnosis, or therapy of disease or for the modification of physiologic function.

Assessing causal connections between agents and disease is fundamental to the understanding of adverse drug reactions. In general, a drug may be considered a contributory cause of an adverse event if, had the drug not been administered, 1) the event would not have happened at all, 2) the event would have occurred later than it actually did, or 3) the event would have been less severe.

All subjects will be monitored for AEs during the study. AEs will be recorded in the subject's source documents from the first dose through 30 days after the last dose. All Grade 1-5 AEs will be captured within the Prometheus, irrespective of relatedness to study drug(s). Hematologic lab abnormalities will not be recorded or reported as adverse except for prolonged myelosuppression as defined by the NCI-CTCAE criteria specific for leukemia, e.g. marrow hypocellularity on day 42 or later (6 weeks) from start of therapy without evidence of leukemia (< 5% blasts), or that results in dose modifications, interruptions or meets the protocol definition of DLT or SAE.

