### 3.1. Rationale for dose and regimen selection

The selection of the starting dose level and regimen is based on the extrapolation of data from cell line efficacy models and toxicology studies in rodents and monkeys.

The DS-1594b Severely Toxic Dose in 10% of animals (STD10) in mice was greater than 300 mg/kg/day and the Highest Non-Severely Toxic Dose (HNSTD) in monkeys was 60 mg/kg/day. The human equivalent dose (HED) of 300 mg/kg/day in mice, based on allometric scaling by body surface area, is approximately 24.3 mg/kg, and using 1/10th of the HED gives a dose of 2.4 mg/kg as the recommended starting human dose for the proposed clinical study. The value of 2.4 mg/kg is lower than a starting dose (3.2 mg/kg) derived from 1/6th of the HED for the HNSTD (60 mg/kg/day) in monkeys. The estimated human systemic exposure at the starting dose exceeds the IC50 of DS-1594b against MV-4-11 human AML cell line (1.97 nM [1.13 ng/mL]), and inhibition of cell proliferation is expected. Therefore, the value of 2.4 mg/kg is considered the appropriate starting dose for the proposed clinical study. No supportive data are available at this stage that would suggest body size-based dosing would reduce human inter-subject variability in PK. Thus, based on an average body weight of 60 kg human, the recommended starting human dose is 140 mg/day. A dosing approach with 70 mg given twice a day will be adopted in order to reduce Cmax while maintaining AUC compared to once-daily dosing to mitigate potential QT interval prolongation risk, given the observed QTc interval prolongation signal seen in monkeys (see Section 2.4.2). In addition, the estimated clinical half-life of DS-1594b is ~ 7 to 8 hours, which also supports a twice daily dosing regimen.

Based on emerging clinical data to assess the PK and safety profile of DS-1594b, the frequency of dosing may be adjusted to once daily (QD), if deemed appropriate and supported by safety data. In this case, dose escalation would follow the same rules as the BID schedule. The SRC

may recommend the enrollment of simultaneous QD and BID dosing regimens or may switch from BID dosing to QD dosing.

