Upon completion of the 8 courses of the Mini-hyper-CVD regimen, subjects may continue DS-1594b orally twice daily (or daily) continuously of each 28-day cycle for up to 2 years during maintenance. The dose will be according to the dose level administered during Cycles 2 through 8. Subjects may be moved from the intensive chemotherapy phase to the maintenance phase with vincristine, steroids, DS-1594b orally twice daily (or daily) continuously prior to completion of 8 cycles of chemotherapy due to frequent infectious complications, or if the subject is intolerant to the chemotherapy (after discussion with the Principal Investigator). If an early transition to maintenance phase is planned, subjects should receive at least 2 cycles of intensive chemotherapy. The reason for early transition to the maintenance phase must be documented in the medical record.

At any time while enrolled in this trial, subjects may be referred for hematopoietic stem cell transplantation at the discretion of the treating physician. DS-1594b will be discontinued at least 2 days prior to the start of the conditioning regimen for hematopoietic stem cell transplantation.

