#### **9.4.5. Analysis of Prior and Concomitant Medications**

Prior and concomitant medications will be coded using the World Health Organization drug dictionary (WHO-DD). Concomitant medications will be summarized by ATC2 class and preferred term for the Safety Analysis Set. Prior medications will be summarized for the Safety Analysis Set. Within each level of summarization, a subject will be counted once if he/she takes one or more medications.

Prior medications are defined as those with a start date prior to the date of first dose of study drug. Concomitant medications are defined as those with a start date greater than or equal to the date of first dose of study drug, or with a start date prior to the date of first dose of study drug and a stop date either after the date of first dose of study drug or marked as “ongoing” or “continuing”. Medications taken prior to the first dose of study drug, but with a missing stop date or with a stop date either on or after the date of the first dose of study drug or marked as “ongoing” or “continuing” will also be considered concomitant medications for the summary. Medications started after the 40-day visit or after start of new anticancer therapy are not considered as concomitant medications. A listing of prior and concomitant medications by subject will also be provided.

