#### **9.4.7. Safety Analyses**

Safety analyses will be performed in the safety population. AEs that occur or worsen relative to the pre-treatment state after the start of study treatment and within 30 days of the last dose of study drug (TEAEs) will be tabulated. AEs will be coded using the Medical Dictionary for Regulatory Activities (MedDRA) terminology and tabulated by body organ group using the MedDRA system organ class (SOC) and by AE term using preferred terms (PTs).

Safety evaluation will include DLTs, serious adverse events, treatment-emergent adverse events, physical examination findings (including ECOG performance status), vital signs measurements, standard clinical laboratory parameters, and ECG parameters (including QTcF).

Safety analyses in general will be descriptive and will be presented in tabular format with the appropriate summary statistics by dose level and in total for Phase 1, and by cohort and in total for Phase 2, unless otherwise stated. Only the treatment emergent assessments (i.e., assessments within the 30 days of last study drug dose) would be used in the analyses unless otherwise specified.

The summary of DLTs in the Dose Escalation parts will be performed based on the DLT Evaluable Set. All other safety summaries and analyses will be performed based on the Safety Analysis Set and subjects will be analyzed according to the actual treatment they received.

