##### **9.4.7.2. Adverse Events**

Adverse events will be assigned grades based on NCICTCAE v5.0.

A TEAE is defined as those AEs with start or worsening date during the treatment period (from first dose date until 30 days after the last dose of study medication). It includes AEs having been absent at pre-treatment; or reemerges during treatment, having been present at baseline, but stopped prior to treatment; or worsens in severity after starting treatment relative to the pre-treatment state, when the AE is continuous.

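### The SAP's 30-day treatment-emergent window does not stop when new antileukemic therapy or transplant conditioning starts, so some safety tables can include toxicity of the next treatment

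*Combined protocol and SAP*

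**What the plan says.** **Collection.** Section 8.10.1 has adverse events entered in "source documents from the first dose through 30 days after the last dose", at all grades and regardless of attribution. Hematologic abnormalities are mostly excluded. The exceptions are prolonged myelosuppression (for example a hypocellular marrow on day 42 or later without leukemia) and events that lead to a dose change or meet the DLT or SAE definition.

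**Analysis.** Section 9.4.7.2 counts an event as treatment-emergent if it starts or worsens "from first dose date until 30 days after the last dose of study medication". Section 9.4.7 restricts the safety analyses in general to treatment-emergent assessments, meaning "assessments within the 30 days of last study drug dose". Neither definition mentions what the subject receives after DS-1594b.

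**Medications.** Section 9.4.5 is the only place in the analysis plan with such a cut: "Medications started after the 40-day visit or after start of new anticancer therapy are not considered as concomitant medications".

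**What can follow DS-1594b.** Section 5.5.1 (Cohort D) permits referral for transplant at any time and states: "DS-1594b will be discontinued at least 2 days prior to the start of the conditioning regimen". Proceeding to transplant is a secondary endpoint in both phases (Table 2). Section 8.9.1 requires treatment to stop for clinically significant progression and sets no interval before salvage therapy. The schedules of events (Tables 32 to 35) include subsequent antileukemic treatment among the follow-up items.

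**The concern.** A treatment-emergent table is read as describing what happened on the study drug and shortly afterwards. In relapsed or refractory acute leukemia, the weeks after the last dose are often the first weeks of something else: salvage chemotherapy, another investigational agent, or conditioning and transplant. Events from that treatment enter the DS-1594b tables under the present definitions.

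The plan also treats the two halves of the same episode differently. A salvage drug started 10 days after the last dose is not a concomitant medication under Section 9.4.5, yet an adverse event on it is treatment-emergent under Section 9.4.7.2. The concomitant-medication summary would not show the treatment that explains the event.

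Safety is a primary objective in Phase 1 and in every Phase 2 cohort (Table 1), and there is no control arm in which the excess would cancel.

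**Working it through.** The plan gives no figure for this point, so there is none to reproduce. The check sets the rules side by side and then works out how much of the window is exposed.

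**1. Is the window cut anywhere?**

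| Section | What it governs | Ends at new therapy? |
|---|---|---|
| 8.10.1 | AE recording | No |
| 8.10.2, 8.10.4 | SAE capture, to 30 days after the last dose | No; the only exception is withdrawal of consent |
| 9.4.7 | TEAE tabulation; treatment-emergent assessments | No |
| 9.4.7.2 | TEAE definition | No |
| 9.4.5 | Concomitant medications | Yes |

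Section 8.10.1 also refers to an institutional leukemia guideline that is not part of the documents, but says the protocol's wording prevails where the two differ.

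**2. How much of the window can belong to the next treatment?**

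- Cohort D transplant: window 30 days, minimum gap 2 days. Overlap is at most 30 − 2 = 28 days.
- Other salvage therapy: no gap is stated. Assuming a start 0 to 14 days after the last dose, the overlap is 30 − 0 = 30 days down to 30 − 14 = 16 days.

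**3. Which outputs are exposed?**

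- Section 9.4.7.2.1 gives related-only versions of the overall and the serious TEAE tables (items 2 and 4). The table of TEAEs associated with death (item 8) has none.
- The special-interest summaries in Section 9.4.7.2.2 (any, Grade 3 or higher, fatal) have no related-only version. Their search terms are broad: Table 27 includes hepatic queries, a broad QT query, falls and presyncope.
- Sections 9.4.7.2.3 and 9.4.7.4 take extreme laboratory and ECG values and include unscheduled ones. Exposure here depends on values being captured after the end-of-treatment visit.

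**4. How large could the effect be?** The documents give no rate of new therapy within 30 days, so any figure is an assumption. Let *b* be the Grade 3 or higher TEAE rate without contamination, *h* the share of subjects starting new therapy in the window, and *q* the chance of a Grade 3 or higher event on that therapy, taken as independent of earlier events. Then

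reported rate = *b* + *h*(1 − *b*)*q*, and excess = *h*(1 − *b*)*q*.

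| Assumed *b* | Assumed *q* | Excess at *h* = 10% | Excess at *h* = 40% | Reported rate |
|---|---|---|---|---|
| 50% | 80% | 0.10 × 0.50 × 0.80 = 4.0 points | 0.40 × 0.50 × 0.80 = 16.0 points | 54% to 66% |
| 50% | 40% | 0.10 × 0.50 × 0.40 = 2.0 points | 0.40 × 0.50 × 0.40 = 8.0 points | 52% to 58% |
| 90% | 80% | 0.10 × 0.10 × 0.80 = 0.8 points | 0.40 × 0.10 × 0.80 = 3.2 points | 90.8% to 93.2% |

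The formula also supposes that these subjects would have had no new Grade 3 or higher event in those weeks without the new therapy. The table shows how strongly the answer depends on the inputs. It is not an estimate for this trial.

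**The case against.** Much of the case against a stronger claim stands.

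- **Treatment-emergent is a time label, not a causal one.** Each event receives a five-level attribution (Section 8.10.1), and related and related-serious tables are planned. A conditioning toxicity judged unrelated stays out of those. This protects part of the output, but not the all-causality, death and special-interest tables.
- **Post-conditioning aplasia will mostly not appear as an adverse event.** A reader might infer that it fills the tables. Section 8.10.1 excludes most hematologic events, although the exceptions for late marrow hypocellularity and for SAEs readmit some. Minimum blood counts in the laboratory summaries are outside that exclusion.
- **The documents do not show that dose selection is distorted.** Escalation uses first-cycle DLTs (Section 3.2), and so does Phase 2 toxicity stopping (Section 9.3). The review committee recommends the RP2D from safety, efficacy and PK/PD data together. No section ties that choice to the 30-day tables.
- **The direction of bias is not established.** A reader might infer that a more active cohort looks more toxic because more of its subjects reach transplant. Non-responders, however, leave for salvage therapy, which works the other way.
- **Pharmacology does not settle the matter.** Section 3.1 says "the estimated clinical half-life of DS-1594b is ~ 7 to 8 hours", so five half-lives are 5 × 7 = 35 to 5 × 8 = 40 hours, inside the 2-day gap. But that estimate precedes human data, Section 2.4.2 reports time-dependent CYP3A inhibition, and Section 5.6.1 says the effect may be delayed. A full 30-day window is defensible as a conservative view in a first-in-human study, which is why the uncut tables should remain.
- **The supporting texts are narrow.** The 2-day rule appears only for Cohort D. The sentence in Section 9.4.5 concerns a medication summary and cites a 40-day visit that the schedules do not contain. Subsequent therapy is recorded elsewhere, so the information is not lost.

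**Conclusion.** The point holds as a gap in the analysis definitions in Sections 9.4.7 and 9.4.7.2. Recording events for 30 days is not at fault. The fault is that everything recorded in those 30 days is labelled treatment-emergent even after another antileukemic treatment has begun, while Section 9.4.5 draws the line at that moment for medications.

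Up to about 28 of the 30 days can be affected for a Cohort D subject going to transplant at the minimum gap. The window is open-ended for other salvage therapy. The exposed outputs are the all-causality, death and special-interest tables, plus any extreme laboratory or ECG values captured in that period. The excess would be mainly non-hematologic or serious events.

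Neither the size of the effect nor its net direction across cohorts can be derived from the documents. The illustrative excess runs from 0.8 to 16 points, wholly on assumed inputs. DLT-based decisions are not affected. This is a low-cost improvement to make before the data are seen, not a threat to the trial's conduct.

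**What to change.** 1. Leave collection in Section 8.10.1 at 30 days after the last dose.
2. In Sections 9.4.7 and 9.4.7.2, end the TEAE window and the treatment-emergent laboratory and ECG window at the earlier of 30 days after the last dose or the day before the first new antileukemic therapy or conditioning. State that agents the protocol itself permits, such as hydroxyurea and intrathecal therapy under Section 5.6.1, do not count as new therapy.
3. Still count events assessed as at least possibly related through day 30, and later related SAEs as Section 8.10.2 already requires them to be reported.
4. Present the uncut 30-day tables alongside as supportive.

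**Cost.** SAP wording, one derived end date and a second set of tables. Subsequent antileukemic treatment is already in the schedules of events. The start date of conditioning is not named there as a separate item, so confirm that the eCRF captures it.

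**Downside.** A delayed DS-1594b effect that is judged unrelated after new therapy starts would appear only in the uncut tables. Subjects who switch early have shorter follow-up in the cut tables, and this shortening is related to outcome. Keeping possibly related events also makes the cut definition depend partly on open-label attribution. Showing both sets of tables lets the reader see how much these matter.
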